The primary outcome of the study is to determine differences in glycemic control as measured by mean daily blood glucose concentration between treatment groups. For each subject, we will take the average of all pre-meal and bedtime glucose values collected after the first day of therapy during the hospital stay (up to 10 days).

Secondary outcomes include differences between treatment groups in any of the following measures:

1. Differences in mean daily glucose in patients admitted to medicine and surgery services.
2. Differences in mean daily glucose in patients with admission HbA1c lower than and higher than 8%.
3. Differences in mean daily glucose in patients with length of stay shorter and longer than 3 and 5 days.
4. Proportion of BG readings within target of 80 mg/dl and 180 mg/dl before meals.
5. Number of BG readings between 80 mg/dl and 180 mg/dl before meals without hypoglycemia.
6. Number of patients with hypoglycemia (defined as a BG < 70 mg/dl) and number of events adjusted by length of stay (event rate).
7. Number of patients with severe hypoglycemia (defined as a BG < 40 mg/dl) and number of events adjusted by length of stay (event rate).
8. Length of hospital stay.
9. Cardiac complications are defined as myocardial infarction, cardiac arrhythmia requiring medical treatment, or cardiac arrest.
10. Acute renal failure defined as a clinical diagnosis with documented new-onset abnormal renal function (increment in serum creatinine > 0.5 mg/dL from baseline).
11. Hospital mortality.

IV.d. Plan. This study will include male or female subjects > 18 years. Due to the design of this study, there will be no run-in period. Upon arrival to the emergency department or medical or general surgical wards, subjects will be screened. Patients with a known history of T2D treated with diet alone, any combination of OADs, and insulin prior to admission will be considered potential candidates for this study. Patients treated with degludec, glargine U300 or with long-acting GLP1-RA (dulaglutide, albiglutide and weekly exenatide) prior to admission will be excluded. Patients admitted with acute or chronic medical illnesses, emergency or elective surgical procedures and trauma would be included in the study. The goal of insulin therapy is to maintain fasting and pre-meal blood glucose levels between 80 mg/dl and 180 mg/dL while avoiding hypoglycemia.

A total of 180 patients with T2D with a blood glucose > 140 mg/dL and < 400 mg/dL will be randomized to receive:

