The primary endpoint for Aim 1 is glycemic control measured by mean daily BG concentration among the two study groups. Blood glucose will be measured before each meal and at bedtime. We will first perform cross-sectional analyses using nonparametric Krustal-Wallis tests (or Wilcoxon tests) or one-way ANOVA, followed by repeated measures ANOVA to estimate and test the difference between the two treatment groups while simultaneously examining mean daily BG across multiple days during treatment. A mixed effect model may be used to further account center effect or other potential confounders for the BG outcome. Stepwise, backward, or forward model selection strategy will be adopted to determine the variables to be included in the final model. Standard diagnostic and model checking procedures will be applied to examine the fit of the developed models.

Analysis of Secondary Endpoints:

Secondary endpoints for Aim 1 in this study include incidence of hypoglycemia, number of hypoglycemic

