events, number of severe hyperglycemia, mean daily fasting BG, daily insulin dose, length of hospital stay, acute renal failure and hospital mortality. Blood glucose will be measured before each meal and at bedtime. For discrete outcomes (such as hypoglycemia outcomes), if the outcome is binary (e.g. with or without hypoglycemia), we will first conduct nonparametric comparisons based on a two-sided Chi-square test (or Fisher's exact test in the presence of low incidence rates), followed by the Cochran-Mantel-Haenszel test, which adjusts for the potential center effect. If the discrete outcome is a count outcome (such as the number of hypoglycemic event), we will perform Poisson regression (or Negative Binomial regression) that adjusts for the length of hospital stay to assess the difference in the count outcome between the treatment groups. We also value the repeated measures analyses based on mixed effect models. This is because they will allow us to assess treatment effect fine tuned according to other confounders of the BG outcomes. By these considerations, we will conduct both types of analyses to provide a thorough evaluation of the hypothesis of interest. For continuous outcomes that are not repeated measures (such as length of hospital stay), we will use two-sample t-tests or nonparametric Wilcoxon tests to compare them between groups. Transformations will be applied if normality violation is detected. Multivariate linear regression will be further conducted to assess the difference in continuous secondary outcomes between the two groups while other relevant covariates. We will use standard model selection and model checking procedures for linear regression to decide the final models and assess their fits to the data.

IV.f. Data and Safety Monitoring Board (DSMB):

The Data and Safety Monitoring Board (DSMB) will review unblended data on safety, treatment compliance, and evaluate the efficacy of the intervention being studied in this clinical trial. The DSMB will meet at 6-month intervals and report on study progress to the IRB.

IV.g. Interim Analysis and Stopping Rules: We plan to perform one interim analysis on the primary endpoint every 6 months and when half of the subjects have been randomized. The trial will be stopped if there is evidence beyond a reasonable doubt of a difference in the rate of death and hospital complications (two-sided alpha level, <0.01) between the treatment groups.

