Subjects with persistent hyperglycemia (≥ 2 glucose readings ≥ 400 mg/dL, ≥ 3 consecutive glucose readings > 280 mg/dL, or with a mean daily blood glucose concentration ≥ 280 mg/dL) and no treatable intercurrent cause for the hyperglycemia has been identified, will be considered as treatment failure and discontinued from the study. If needed, subjects will be started on continuous insulin infusion.

VII. Study Sites: This study will be performed at Grady Memorial Hospital, Emory University Hospitals, Atlanta, GA, Minneapolis Medical Research Foundation-Hennepin Medical Center, Minneapolis, and The Cleveland Clinic Foundation, Ohio.

VIII. CLINICAL MANAGEMENT GUIDELINES

VIII.a. Admission Laboratory Studies

Standard of care laboratory studies including glucose, HbA1C, and chemistry will be measured on admission and as determined by the treating physician.

For **research purposes** a blood sample will be obtained to measure HbA1C at 1 month and 3 months after discharge. In addition, a urine pregnancy test will be performed, when clinically indicated prior to randomization (in female subjects of child bearing potential only).

VIII.b. Assessment and Monitoring of Hospital Mortality

The investigators and research team will follow study subjects daily and the presumed cause of death will be recorded. Information on the attending physician’s summary of events surrounding subject’s demise will also be documented.

VIII.c. Assessment and Monitoring of Nosocomial Infections

Nosocomial infections will be diagnosed based on standardized CDC criteria (40). New nosocomial infections will not be diagnosed until 48 hours after study initiation to minimize the chance that the infection was actually present (but undiagnosed) prior to study initiation.

The investigators will review each subject’s records regarding potential new infection diagnosis daily on each weekday from Monday to Friday. Data from the weekends will be collected on the following Monday. The coded infection diagnosis and the presumed causative microorganism will be determined daily on a Monday to Friday basis, with weekend data entered on the following Monday.

Aim 1. Inpatient Arm – Flow Chart

Visit Type	Hosp- Day 1	Hosp- Day 2	Hosp- Day 3	Hosp- Day 4	Hosp- Day 5	Hosp- Day 6	Hosp- Day 7	Hosp- Day 8	Hosp- Day 9	Hosp- Day 10
Visit #	1	2	3	4	5	6	7	8	9	10
Time-days	1	2	3	4	5	6	7	8	9	10
Inf. consent	x									
Inclusion/excl criteria	x									
Randomization	x									

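### Repeated measures ANOVA does not suit unequal numbers of hospital days: let the per-patient average decide and use a mixed model for the across-days analysis

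*Combined protocol and SAP*

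**What the plan says.** **Endpoint.** Section IV.c reduces each patient to one number, the "average of all pre-meal and bedtime glucose values collected after the first day of therapy during the hospital stay (up to 10 days"). The same section lists as a secondary outcome "Differences in mean daily glucose in patients with length of stay shorter and longer than 3 and 5 days", and also lists length of stay itself.

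**Sample size.** Section IV.g, Sample Size and Power Calculations, uses a one-sided two-sample t-test, a margin of 18 mg/dl, an SD of 45 mg/dl and a true difference of zero. It arrives at 78 per group, raised to 90 for 10% attrition.

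**Analysis.** Section IV.g, Analysis of Primary Endpoint, opens with "We will first perform cross-sectional analyses using nonparametric Krustal-Wallis tests (or Wilcoxon tests) or one-way ANOVA". The next step is "followed by repeated measures ANOVA to estimate and test the difference between the two treatment groups", looking at daily means over multiple days. Then: "A mixed effect model may be used to further account center effect or other potential confounders for the BG outcome".

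**Shortened series.** Under Treatment Failure Criteria, patients with persistent hyperglycemia and no treatable cause "will be considered as treatment failure and discontinued from the study". Section VI.d adds withdrawals after randomization, for example for corticosteroid treatment.

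The primary analysis text does not say which days enter the repeated measures ANOVA, what happens to days after discharge or discontinuation, which covariance structure applies, or which step decides the primary question.

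**The concern.** Classical repeated measures ANOVA needs the same set of days for each patient; a patient who lacks one analysed day is left out. Here a patient contributes anything up to nine daily means (days 2 to 10), and discharge or discontinuation sets the number. A complete-case run over many days would keep only long-stay patients, and the sample would shrink well beyond the 10% allowed for attrition.

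A linear mixed model fitted to all observed daily means avoids this exclusion. The primary analysis mentions one only as an option, for center and confounders, and not because the series are unequal.

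The repeated measures ANOVA is also the only step in that paragraph said to estimate the treatment difference, and a non-inferiority margin needs an estimate in mg/dl with a bound. If an analyst took this step as decisive and ran it in its classical form, power and the population described would both depend on how many patients stayed long enough.

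**Working it through.** **1. Reproduce the plan's figure.** Inputs from section IV.g: margin 18, SD 45, true difference 0, power 80%, one-sided test. Alpha is not stated; one-sided 0.05 is inferred because it returns the plan's number.

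n per group = 2 × [45 × (1.645 + 0.842) / 18]² = 2 × 6.216² = 77.3, rounded up to 78. This matches. One-sided 0.025 would give 99.

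**2. Power after attrition.** 90 × 0.9 = 81 per group. Power = Φ(18 / (45 × √(2/n)) − 1.645) = Φ(0.4 × √(n/2) − 1.645). At n = 81 this is Φ(2.546 − 1.645) = Φ(0.901) = 0.82.

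**3. Share of patients with every day observed.** The documents give no minimum, mean or distribution of stay, so both sets below are assumptions.

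*Set A: geometric stays with mean m.* P(stay ≥ k) = (1 − 1/m)^(k−1).

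| Mean stay m | Through day 5 | Through day 10 |
|---|---|---|
| 4 | 31.6% | 7.5% |
| 5 | 41.0% | 13.4% |
| 7 | 54.0% | 25.0% |

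Of 180 randomized patients, 0.075 × 180 ≈ 14 to 0.25 × 180 = 45 would have data through day 10. This form allows one-day stays (a fraction 1/m), which supply no value after day 1.

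*Set B: minimum stay 2 days, median M.* P(stay ≥ d) = q^(d−2), with q = 0.5^(1/(M − 1.5)). Example, M = 4: q = 0.5^(1/2.5) = 0.758; through day 10, q⁸ = 0.109, so 81 × 0.109 = 8.8 per group; power = Φ(0.4 × √4.4 − 1.645) = Φ(−0.806) = 0.21.

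| Median stay | Complete to day 5: share, n per group, power | Complete to day 10: share, n per group, power |
|---|---|---|
| 4 | 43.5%, 35.3, 51% | 10.9%, 8.8, 21% |
| 5 | 55.2%, 44.7, 60% | 20.5%, 16.6, 31% |
| 6 | 63.0%, 51.0, 65% | 29.2%, 23.6, 39% |
| 7 | 68.5%, 55.5, 68% | 36.5%, 29.6, 46% |

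**4. Without a stay distribution.** If 80% of the 81 per group are complete, power is 74%; 50% gives 56%; 30% gives 40%. These figures and the table hold the SD at 45 and use the normal approximation, which is slightly optimistic for the smallest groups.

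**5. Methods that use all observed days.** A simulation with Set B stays, 81 per group, between-patient SD 40, day-to-day SD 35 and 150 replicates per setting gave these power ranges:

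| Analysis | Power |
|---|---|
| t-test on the per-patient average | 79% to 82% |
| Random-intercept mixed model | 77% to 85% |
| Complete cases to day 5 | 53% to 69% |
| Complete cases to day 10 | 25% to 50% |

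The simulation error near 80% is about √(0.8 × 0.2 / 150) = 3.3 percentage points, so the first two rows do not differ meaningfully. Both stay near the planned power.

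**The case against.** The strongest reply is that the primary endpoint never needed a full set of days. Section IV.c takes one average per patient, the sample size rests on a two-sample t-test of such a quantity, and the first listed analysis is cross-sectional. Any patient with a value after day 1 contributes. All of this stands.

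It is also fair that the plan nowhere announces a complete-case analysis or requires all of days 2 to 10. The name repeated measures ANOVA is sometimes used loosely for models fitted to all observed days, and the secondary-endpoint section says "We also value the repeated measures analyses based on mixed effect models". A reader might nevertheless infer that every patient without a full set of days would be dropped, and that the stated power and target population are therefore lost. The documents do not support that: exclusion follows only from the classical form, and the power statement is tied to the per-patient average.

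The reply does not remove the point. The mixed-model sentence sits under secondary endpoints and is justified there by confounders, so it does not settle the primary analysis. Listing the cross-sectional test first does not make it decisive either. Its rank-test options do not by themselves give a mean difference in mg/dl to set against the margin, and the step described as estimating the difference is the repeated measures ANOVA.

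**Conclusion.** The point holds as a poorly suited named method, not as a demonstrated loss of patients. The number of days is unequal by design, the primary analysis does not say how that is handled, and the better-suited model is optional.

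For the section IV.c average, the planned power of about 82% at 81 per group is intact. If the repeated measures ANOVA were read as the deciding test and run on complete cases, power would be about 21% to 46% over days 2 to 10, or 51% to 68% over days 2 to 5. These ranges rest on assumed stays (2-day minimum, median 4 to 7 days), an SD of 45 mg/dl and one-sided alpha 0.05.

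Two further inferences should be avoided. The documents give no shortest stay and do not say that discharge depends on glucose; only discontinuation for treatment failure is tied to it. Bias in the treatment difference has not been shown: if stay depends on glucose in the same way in both arms and the true difference is zero, the expected difference is zero by symmetry. Stays that differ by arm were not examined.

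**What to change.** 1. Name one deciding analysis for Aim 1: the between-group difference in the section IV.c per-patient average, with its confidence bound read against 18 mg/dl. State alpha. If it is one-sided 0.05, as the 78 per group implies, the matching interval is a 90% CI.
2. Replace the repeated measures ANOVA with a prespecified linear mixed model as the supporting across-days analysis. Fit it by restricted maximum likelihood to all observed daily means from day 2 to day 10, with a patient random effect and fixed effects for treatment, day, prior insulin use (the randomization stratum) and site.
3. State the covariance structure, and say that days observed before discharge or discontinuation are kept.

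The cost is SAP wording; sample size and data collection do not change. The downside is that the mixed model assumes days after discharge or discontinuation are missing at random given observed glucose. It also weights patients differently from the simple average. For both reasons it should support the per-patient average and not replace it.

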
Group 1. Basal bolus with glargine U300 once daily and glulisine insulin before meals (n=90).

Group 2. Basal bolus with glargine U100 once daily and glulisine insulin before meals (n=90).

IV.d. Basal Bolus Insulin Protocol.

Patients will be treated with a basal bolus insulin regimen as previously reported (15, 16, 39). In brief, subjects treated with insulin prior to admission will receive 80% of the total daily outpatient insulin dose given. Insulin naïve patients will discontinue oral agents and will receive a starting total daily dose (TDD) of 0.4 U/kg/day for BG between 140 mg/dl and 200 mg/dL and 0.5 U/kg/day for BG between 201 mg/dl and 400 mg/dL. The starting TDD will be reduced to 0.3 U/kg/day in patients \geq 70 years or with a GFR < 60 ml/min. Both groups will be treated with bolus regimen given half of TDD as basal (glargine U300 or U100) once daily and half as insulin glulisine divided in three equal doses before meals. Patients with poor oral intake or to be kept NPO will receive the basal dose, but prandial dose will be held (32). Insulin dose will be adjusted daily to maintain a fasting and pre-dinner BG between 80 mg/dl and 180 mg/dl.

IV. e Treatment randomization. This is an open label randomized controlled trial. Patients will be randomized 1:1 consecutively using a computer generated randomization table provided by [name], statistician at the Emory School of Public Health. The randomization table will be mailed to the research pharmacist at each institution who will be in charge of the randomization and group assignment. A research pharmacist at each institution will follow a computer-generated block randomization table based on prior insulin use (yes/no).

IV.f TREATMENT PROTOCOL - Basal Bolus Insulin Regimen with Glargine Once Daily plus Glulisine before Meals

Patients Treated with Insulin Prior to Admission

- Discontinue oral antidiabetic drugs on admission.

Subjects treated with insulin prior to admission will receive 80% or 100% of the total daily dose (TDD) given as basal bolus regimen. **Starting Insulin Doses:**

- Randomization BG <200mg/dl-give 80% of the TDD*
- Randomization BG>200mg/dl-give 100% of the TDD*
- Half of TDD will be given as basal (glargine U300 or U100) and half as rapid-acting insulin.
- Glargine U300 and U100 will be given once daily, at the same time of the day.
- Patients will receive the full-dose of glargine (even if NPO) the day of surgery or diagnostic procedure(s).

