- If a patient develops hypoglycemia (BG <70 mg/dL), the insulin TDD (basal and prandial) should be decreased by 20%.
- If a patient develops severe hypoglycemia (BG <40 mg/dL), the insulin TDD (basal and prandial) should be decreased by 30-40%.

IV.g. Data Analysis:

Aim 1. To determine differences in inpatient glycemic control, as measured by mean daily blood glucose concentration and frequency of hypoglycemia, in general medicine and surgery patients with T2D treated with basal bolus regimen with glargine U300 and U100 plus glulisine insulin before meals.

Due to the lack of efficacy and safety data with the use of glargine U300 in the inpatient setting, periodic conduct interim analyses will be conducted every 6 months to monitor the primary outcome and rate of hypoglycemia, and to modify the study design regarding interval of administration and dosage adjustment for basal insulin (see page 9, Data Safety Monitoring Plan, sections IV. f. and IV.g.).

Sample Size and Power Calculations:

The primary endpoint in this study is glycemic control measured by mean daily BG concentration. To show the non-inferiority of glargine U300 and U100 in terms of glycemic control, we set the equivalence margin as 18 mg/dl (1 mosm/l), from a view that a difference <18 mg/dl is usually not considered as clinically significant (12, 14, 16). Based on the results from Rabbit medicine and surgery trials, it is reasonable to assume the standard deviation of mean daily BG is bounded above by 45 mg/dl. Assuming the true BG difference between the treatment groups is zero, and using one-sided, two-sample t-tests, we require 78 subjects for each treatment group to achieve 80% power. Accounting for 10% attrition rate, we would need 90 patients per treatment group, which means 180 subjects in total, to achieve >80% power in Aim 1.

Analysis of Primary Endpoint:

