We plan to study a total of 180 randomized patients with a known history of T2D, age > 18 years, treated with diet alone, any combination of oral antidiabetic agents, GLP1-RA (except long-acting agents: albiglutide, albiglutide and weekly exenatide) or insulin therapy (except degludec or glargine U300). Patients included within this study will be determined by the set of inclusion and exclusion criteria.

VI.b. Inclusion Criteria:

1. Males or females between > 18 years admitted to a general medicine or surgical service.
2. Known histories of T2D treated with either diet alone, oral monotherapy, any combination of oral antidiabetic agents, short-acting GLP1-RA (exenatide, liraglutide) or insulin therapy with the exception of degludec and glargine U300.
3. Subjects must have a randomization BG > 140 mg and < 400 mg/dL without laboratory evidence of diabetic ketoacidosis (bicarbonate < 18 mEq/L, pH < 7.30, or positive serum or urinary ketones).

VI.c. Exclusion Criteria:

1. Subjects with increased BG concentration, but without a known history of diabetes.
2. Admission or pre-randomization BG ≥ 400 mg/dl
3. Patients treated with degludec or glargine U300, or with long-acting weekly GLP1-RA (weekly exenatide, dulaglutide or albiglutide).
4. Patients with acute critical or surgical illness admitted to the ICU or expected to require admission to the ICU.
5. Patients with clinically relevant hepatic disease (diagnosed liver cirrhosis and portal hypertension), corticosteroid therapy, or impaired renal function (eGFR < 30 ml/min).
6. Mental condition rendering the subject unable to understand the nature, scope, and possible consequences of the study.
7. Female subjects who are pregnant or breast-feeding at time of enrollment into the study.

VI.d. Withdrawal Criteria

1. The subject may withdraw at will at any time.
2. The subject may be withdrawn from the trial at the discretion of the investigator due to a safety concern or if judged non-compliant with trial procedures or included in contravention to the inclusion and/or exclusion criteria.
3. Subject admitted to the ICU who required continuous intravenous insulin infusion to maintain glycemic control.
4. Pregnancy or intention to become pregnant.
5. Treatment with oral or injectable corticosteroid (equivalent or higher than prednisone 5mg/day), parenteral nutrition and immunosuppressive treatment after randomization.

Treatment Failure Criteria

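### No analysis is named as the one that decides the 18 mg/dl comparison; one prespecified adjusted regression would settle it at almost no cost

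*Combined protocol and SAP*

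**What the plan says.** All references are to the combined protocol and SAP.

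- **Outcome (IV.c).** "For each subject, we will take the average of all pre-meal and bedtime glucose values collected after the first day of therapy", for up to 10 hospital days. This gives one value per patient.
- **Margin and sizing (IV.g, Sample Size and Power Calculations).** "we set the equivalence margin as 18 mg/dl", and "using one-sided, two-sample t-tests, we require 78 subjects for each treatment group to achieve 80% power". The alpha level is not stated.
- **Primary analysis (IV.g, Analysis of Primary Endpoint).** "We will first perform cross-sectional analyses using nonparametric Krustal-Wallis tests (or Wilcoxon tests) or one-way ANOVA, followed by repeated measures ANOVA". Then: "A mixed effect model may be used to further account center effect or other potential confounders for the BG outcome". Then: "Stepwise, backward, or forward model selection strategy will be adopted to determine the variables to be included in the final model". The paragraph does not mention the margin, a confidence interval, the t-test, a list of candidate covariates or a selection threshold.
- **Data known at baseline.** Randomisation is blocked on prior insulin use (IV.e). Randomisation glucose is an eligibility criterion (VI.b: "Subjects must have a randomization BG > 140 mg and < 400 mg/dL"), so it is on record for every patient. No analysis names either one.
- **Aim 2 (V.g.2).** A t-test, Wilcoxon test or one-way ANOVA is followed by a planned multivariable linear regression, with the same selection wording.

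**The concern.** The sizing paragraph ties the margin to one test, and the analysis paragraph offers several others without saying which one decides. Rank tests and ANOVA F tests, as usually run, test for no difference and do not address an 18 mg/dl margin. A reader therefore cannot tell which estimate and which limit will be set against 18.

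Two modest things are at stake. First, the trial is open label and the primary endpoint is looked at during the trial, so an unfixed choice among analyses weakens the credibility of a non-inferiority claim and could raise its error rate. Second, if the deciding analysis is unadjusted, any prognostic information in the stratum and randomisation glucose goes unused.

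**Working it through.** **1. Reproduce the stated sample size.** Inputs from IV.g: margin 18, SD 45, true difference 0, one-sided test, 80% power. With one-sided alpha 0.05, n = 2 × [45 × (1.645 + 0.842) / 18]² = 77.3, so 78 per group. The exact t calculation also gives 78, with power 0.800. One-sided 0.025 would need 99, so 5% is the level inferred here. With 90 per group and 10% attrition, 90 × 0.9 = 81 are evaluable.

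**2. Power with and without adjustment.** If the covariates explain a share R² of the variance, the residual SD is SD × √(1 − R²), and power follows from the noncentral t with noncentrality 18 / (residual SD × √(2/81)). The documents give no R², so 0 to 25% is assumed. SD 45 is the upper bound in IV.g. SD 32 is the basal-bolus spread reported for the earlier surgery trial in section III.

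| R² | Residual SD (from 45) | Power, SD 45 (formula) | Power, SD 32 (formula) | Unadjusted t-test, SD 45 (simulated) | Fixed model, SD 45 (simulated) |
|---|---|---|---|---|---|
| 0 | 45.0 | 81.3% | 97.3% | 81.2% | 80.2% |
| 10% | 42.7 | 84.8% | 98.3% | 81.9% | 83.7% |
| 20% | 40.2 | 88.3% | 99.0% | 82.6% | 87.4% |
| 25% | 39.0 | 90.0% | 99.3% | 82.5% | 89.3% |

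The simulation (20,000 runs) assumed 162 patients, blocks of 4 in two equal prior-insulin strata, a mean of 3.7 assessed days, day-to-day correlation 0.5, and four sites with no effect. It includes the cost of the site terms, and it lets the unadjusted test benefit from the stratified balance. Both make the gain a little smaller than the formula suggests. At R² = 0 the fixed model loses 81.2 − 80.2 = 1.0 point.

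**3. Compare with the plan's own optional mixed model.** A separate simulation under the same settings (4,000 runs, Monte Carlo error about 0.6 points) gave these powers at R² 0/10/20/25%:
- Backward-selected, weighted mixed model: 82.8/85.5/89.5/90.9%.
- Fixed regression on unweighted patient means: 79.7/83.6/87.7/89.6%.
- Difference: 3.1/1.9/1.8/1.3 points in favour of the mixed model, which allows for unequal stays. Its weights were taken as known, which favours it slightly.

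**4. Error at the margin (true difference 18, SD 45, one-sided 5%).** Across R² 0 to 25%:
- t-test alone: 4.0-5.0%.
- Repeated measures alone: 4.0-5.1%.
- Backward-selected model alone: 5.0-5.2%.
- Fixed regression alone: 4.8-4.9%.
- Success claimed if any of t-test, repeated measures or selected model succeeds: 6.0-6.8% over two simulations.
- The same with a Wilcoxon test on data shifted by 18 added: 6.7-7.3%. This moves to 6.4-7.6% across day-to-day correlation 0.3 to 0.7, right-skewed data and SD 32.

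**The case against.** **The margin test is already implied.** IV.c gives one mean per patient, the sizing paragraph names a one-sided two-sample t-test, and one-way ANOVA with two groups compares the same means. On this reading only a linking sentence is missing. This stands in part: it narrows the gap but does not close it, because the primary-analysis paragraph omits the t-test and the margin and adds further analyses without ranking them.

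**The error inflation depends on a practice the plan does not describe.** This stands. The plan gives a sequence, its rank tests and ANOVA are alternatives, and the shifted Wilcoxon test appears nowhere in it. A reader might infer that the plan allows a claim on any success; it says no such thing. A reader might also infer that data-driven selection by itself breaks the test. Under the assumptions used, selection alone leaves error near 5%.

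**The power gain depends on the comparator.** This stands. Against the unadjusted analyses there is a gain; against the plan's optional selected mixed model there is none.

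**The gain rests on an assumed R².** This also stands. Randomisation glucose is restricted to a range, sets starting doses for many patients and is followed by daily titration, so its relation to later mean glucose may be weak.

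**Conclusion.** The concern holds as a modest improvement. The plan does not say which analysis is compared with 18 mg/dl, leaves covariates to data-driven selection, and names neither the blocking factor nor randomisation glucose.

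The main benefit of fixing one analysis is that it removes the choice: about 6-7% error instead of 5% if any listed analysis could carry the claim. The second benefit is conditional. At SD 45 and 81 per group, power rises from about 81% unadjusted to 85-90% by formula if the covariates explain an assumed 10-25% of variance. At SD 32 power is already about 97% and the gain is 1-2 points. The optional mixed model may be 1-3 points more powerful than the proposed regression.

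It would be tempting to conclude that the trial is undersized or its test invalid. The documents do not support either conclusion: 78 per group reproduces, and the unadjusted test is valid and if anything conservative. The R² values, stay lengths and day-to-day correlation are assumptions, the 5% level is inferred, and the power figures are not carried over to Aim 2.

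**What to change.** In IV.g, name one primary analysis with no variable selection: linear regression of each patient's mean glucose (as defined in IV.c) on treatment, prior insulin use, site and continuous randomisation glucose. State that non-inferiority is shown if the upper limit of the one-sided 95% confidence interval for U300 minus U100 is below 18 mg/dl. Write the alpha level into the plan, since 5% is only inferred from the 78 per group. Label the rank tests, ANOVA, repeated-measures, mixed and selected models as supportive. In V.g.2, fix the covariates of the regression already planned for Aim 2 in the same way. The change should be made before any further comparison by arm.

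The cost is wording only, since all the variables are already collected. The model uses about five of some 160 degrees of freedom: one for prior insulin use, three for the four sites in section VII, and one for randomisation glucose. It loses about 1 point of power at SD 45 if none of them is prognostic, and it forgoes the 1-3 points that the mixed model might add.
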